12.1.2 Local Skin Reactions

Local skin reaction scores (redness, swelling, burning, itching, and vesiculation) at each visit will be summarized using frequency tables for the safety, PK, and non-PK populations. Additionally, redness and swelling severity scores will be summarized using descriptive statistics (mean, standard deviation [SD], median, and minimum, and maximum). Subjects with a severity score worse than baseline will also be summarized at each post-baseline visit. The worst score and the last score during the post-baseline period will also be summarized.

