Criteria for evaluation: Safety: Adverse events will be collected as spontaneous reports by the subjects and as observations by the investigators. The collection of AEs should begin following the subject's completion of the consent/assent process to participate in the study. Local skin reactions (redness, swelling, burning, itching, and vesiculation) will be reviewed with the subject starting at the Baseline Visit (after study drug application at the investigational center) and continuing through the last study visit. The presence or absence of burning, itching, and vesiculation will be reported simply as "yes" or "no". The worst instances of redness and swelling observed since the previous study visit will be reported using a 4-point scale (where 0 = None, 1 = Mild, 2 = Moderate, and 3 = Severe). Blood and urine samples will be collected for routine clinical laboratory tests (hematology, serum chemistry, and urinalysis) within the 42 day Screening visit window. These samples will be collected again at Week 48, or at Day 28 for PK subjects who consented to only the 4-Week trial. Any clinically significant abnormalities in safety laboratory test results that are present at the last treatment visit (Day 28/Week 48/Early Termination) will be followed to resolution (ie, return to normal values or to the baseline state) or until clinically stable as determined by the investigator. Vital sign measurements (sitting blood pressure, respiration, pulse, and temperature) will be obtained at Baseline and weeks 12, 24, 36, and 48 or at Day 28 for PK subjects who consented to only the 4-Week trial. An abbreviated physical examination will be performed at Baseline and Week 48, and at Day 28 for PK subjects who consented to only the 4-Week trial; as part of the examination, height and weight will be measured at Baseline and Week 48. Urine pregnancy tests will be performed for all FOCBP at the Screening Visit and at each subsequent study visit. If a subject becomes pregnant during the treatment period, the study drug will be discontinued immediately, the subject will be discontinued from the study, and the investigator will notify the sponsor. The pregnancy will be followed to term with the outcome reported to the sponsor. Efficacy will be assessed to evaluate compliance with treatment as part of the safety assessment. The efficacy variables evaluated in this study include microscopic KOH examination and mycological culture outcomes of the target great toenail, percent involvement of the target great toenail, growth of the target great toenail, and assessments of the nontarget toenails. Pharmacokinetics: Concentrations of efinaconazole and metabolites (H3 and H4), along with other relevant PK parameters, will be assessed based on blood samples collected at Days 28 and 29. The specific collection time points are predose on Day 28 and 2, 4, 12, and 24 hours postdose.

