Photography: Close-up photographs of the subject's target great toenail will be used for documentation purposes only and will not be used for determinations of eligibility or any study-related activities.

Statistical Methods:**Safety:**

All subjects who receive at least 1 confirmed dose of study drug will be included in the safety analysis set. No imputations will be made for missing safety data. The primary safety objective will be considered met when approximately 40 evaluable subjects have been treated for 48 weeks.

All AEs occurring during the study will be recorded and classified using the Medical Dictionary for Regulatory Activities (MedDRA). Treatment-emergent adverse events (TEAEs) are those AEs with an onset on or after the date of first study drug application. All TEAEs will be summarized by the number of subjects reporting each TEAE, the associated system organ class and preferred term, the severity, and the relationship to study drug for the Safety, PK and Non-PK populations. Each subject will be counted only once within a system organ class or a preferred term using the event with the greatest severity or causality, respectively, within each category.

Serious adverse events (SAEs) will be summarized by the number of subjects reporting each SAE, the associated system organ class and preferred term, the severity, and the relationship to study drug for the Safety, PK and Non-PK populations.

Local skin reaction scores (redness, swelling, burning, itching, and vesication) at each study visit will be summarized using frequency tables for the Safety, PK and Non-PK populations. Additionally, redness and swelling severity scores will be summarized using descriptive statistics (mean, standard deviation [SD], median, and minimum and maximum). Subjects with a severity score worse than baseline will also be summarized at each postbaseline study visit. The worst score and the last score during the post-baseline period will also be summarized.

Results of safety laboratory parameters and vital sign measurements will be summarized at each study visit using descriptive statistics or frequencies and percentages, as appropriate, for the Safety, PK and Non-PK populations. Changes from baseline in safety laboratory values will be summarized by treatment group at Week 48 using descriptive statistics. In addition, changes from baseline in safety laboratory values will be summarized using shift tables according to normal ranges.

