12. Select target great toenail in each eligible subject for efficacy assessments. Where both great toenails are study-eligible (including percent involvement, KOH-positive, and culture-positive results), the toenail with the greater percent affected area at the Baseline Visit will be selected as the target great toenail prior to enrollment in the treatment period. In the instance where the percent affected area is the same for both study-eligible great toenails at the Baseline Visit, the investigator may choose either great toenail to be the target great toenail.
13. Inscribe a transverse notch in the great toenail at the proximal nail fold with a file or scalpel. This will be used as a marker at subsequent visits for determining new toenail growth.
14. Perform the investigator's assessment of the nontarget toenails for the presence or absence of onychomycosis. Subjects in the PK subset must have at least 4 toenails other than the great toenails with onychomycosis.
15. Take close-up photographs of the target great toenail. The first photograph will be taken after toenail clipping. After that photograph is taken, the investigator/evaluator will use a fine tipped marker to outline the area affected on the target great toenail. When the marker ink has dried, a second close-up photograph will be taken.
16. Review inclusion/exclusion criteria. If the subject continues to meet all inclusion criteria and none of the exclusion criteria, enroll the subject in the treatment period.
17. Obtain 1 bottle of study drug and weigh the bottle. Record the assigned bottle number for the study drug in the subject's source document and on the appropriate eCRF. Dispense the bottle to the subject and their parent/legal guardian (complete the label and required records). For subjects in the PK subset, 2 bottles of study drug should be obtained. The bottles should be weighed separately and recorded as separate entries, as described above.
18. Instruct the subject and their parent/legal guardian on diary completion and dispense diary.
19. The subject or their parent/legal guardian will apply the first dose of study drug in the investigational center. Instruct the subject and their parent/legal guardian in the proper

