application technique for the study drug and provide the appropriate Subject Instruction Sheet with dosing instructions (ie, for non-PK or PK subjects), depending on whether the subject is enrolled in the PK subset. Record any AEs following the initial treatment application.

20. Record local skin reactions. Instruct the subject and their parent/legal guardian to report local skin reactions (if any) at each study visit.
21. Schedule the next study visit (Visit 3 [Week 4, Day 28]) in 28 days (\pm 5 days).

Note: (\pm 5 days) only applies to Non-PK subjects, PK subset only has a (\pm J day) visit window

- For subjects in the PK subset, Visit 3 (Week 4, Day 28) to Visit 3A (Week 4, Day 29) remind subjects not to apply study drug the night prior to their Visit 3 (Week 4, Day 28) visit.

11.1.3 Visit 3 (Week 4, Day 28 [\pm 5 days]), Visit 4 (Week 5 [\pm 5 days]), Visit 6 (Week 16 [\pm 5 days]), Visit 7 (Week 20 [\pm 5 days]), Visit 9 (Week 28 [\pm 5 days]), Visit 10 (Week 32 [\pm 5 days]), Visit 12 (Week 40 [\pm 5 days]), Visit 13 (Week 44 [\pm 5 days])

Visits are to be scheduled in reference to Visit 2 (Baseline).

The following procedures will be conducted at this visit:

1. Record any AEs (query subjects and their parents/legal guardians, "Are there any changes in your health since the last visit?").
2. Record local skin reaction scores reported by the subject and parent/legal guardian.
3. Review concomitant medications.
4. Clip the toenails.
5. Measure the target great toenail growth since the Baseline Visit (distance from proximal nail fold to transverse notch). If the most recently applied notch has grown out or has been clipped off, inscribe a new notch adjacent to the proximal nailfold.
6. Collect the diary and study drug bottle from the subject and/or their parent/legal guardian. Weigh the used bottle of the study drug. Record the number of missed doses from the subject diary and review compliance with the subject.
7. Conduct a urine pregnancy test on FOCBP subjects (discontinue any subject from the study who has a positive test result)
8. Obtain 1 bottle of study drug and weigh the bottle, complete the label and drug log, and dispense the bottle to the subject and their parent/legal guardian. Review the dosing instructions with the subject. (Subjects in the PK subset will not be dispensed study drug this day).
9. Dispense diary. (Subjects in the PK subset will not be dispensed a diary this day.)
10. Schedule the next study visit.

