11.2 Study Evaluations

11.2.1 Local Skin Reactions

Tolerability will be evaluated through assessment of local redness, swelling, burning, itching, and vesication in the selected treatment areas on the toes. Each sign or symptom is to be reviewed with the subjects and their parents/legal guardians after the first application of the study drug at the Baseline Visit and at each follow-up visit through Week 52. The subjects and their parents/legal guardians should assess each reaction based on the worst reaction experienced since the prior visit using the following scales:

Reaction	Score
Redness, Swelling	0 = None 1 = Mild 2 = Moderate 3 = Severe
Burning, Itching, and Vesication	Yes or No

Occurrence of vesication will always be reported as an AE. Any other sign or symptom will be reported as an AE only if it requires concomitant therapy or results in a temporary interruption or permanent discontinuation of the study drug due to discomfort.

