12.1 Assessment of Safety

12.1.1 Adverse Events

All AEs that occur during the study will be recorded and classified using the Medical Dictionary for Regulatory Activities (MedDRA). Treatment-emergent adverse events (TEAEs) are those AEs that occur or worsen on or after the date of first study drug application. All TEAEs will be summarized by the number of subjects reporting each TEAE, the associated system organ class and preferred term, the severity, and the relationship to study drug for the safety, PK, and non-PK populations. Each subject will be counted only once within a system organ class or a preferred term using the event with the greatest severity or causality, respectively, within each category.

All SAEs will be summarized by the number of subjects reporting each SAE, the associated system organ class and preferred term, the severity, and the relationship to study drug for the safety, PK, and non-PK populations.

All information pertaining to AEs noted during the study will be listed by subject and will include the verbatim term given by the investigator, the associated system organ class and preferred term, the start and stop (if stopped) dates, the seriousness, and the severity of the event. Additionally, any action taken with the study drug, any corrective treatment administered, the outcome, and the relationship to study drug as well as a list of subjects who prematurely discontinue from the study due to an AE will be provided.

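### The only Baseline Visit skin reaction score is taken after the first dose, so the worse-than-baseline count for redness and swelling leaves out first-dose reactions that persist at the same or a lower grade

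*Combined protocol and SAP*

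**What the plan says.** References are to the latest protocol version in the combined file.

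**Timing of the first score.** Three places agree:
- Section 11.1.2, step 19: "The subject or their parent/legal guardian will apply the first dose of study drug in the investigational center". Step 20 follows: "Record local skin reactions. Instruct the subject and their parent/legal guardian to report local skin reactions (if any) at each study visit".
- Section 11.2.1 has the signs reviewed "after the first application of the study drug at the Baseline Visit and at each follow-up visit through Week 52".
- The synopsis (Criteria for evaluation, Safety) has the review "starting at the Baseline Visit (after study drug application at the investigational center").

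None of the 18 Screening steps in section 11.1.1, and none of Baseline steps 1 to 18, grades redness or swelling.

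**Analysis.** Section 12.1.2 plans by-visit frequency tables, descriptive statistics for redness and swelling, the worst and last scores over the post-baseline period, and the comparison "Subjects with a severity score worse than baseline will also be summarized at each post-baseline visit". The synopsis repeats the comparison: "Subjects with a severity score worse than baseline will also be summarized at each postbaseline study visit". Neither place defines baseline for these scores.

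**Adverse event rules.** Vesiculation is always an AE. For the rest, section 11.2.1 says: "Any other sign or symptom will be reported as an AE only if it requires concomitant therapy", or if it leads to interruption or discontinuation of study drug. Section 12.1.1 defines treatment-emergent events as "AEs that occur or worsen on or after the date of first study drug application".

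**The concern.** A change-from-baseline summary is meant to separate what the drug did from what was already there. Here the reference is taken once the drug is on the skin. A first-dose reaction raises the reference, and the same reaction seen later then looks like no change. The protocol is also inconsistent with itself: a Day 1 post-dose event is on-treatment for AEs, yet the Day 1 post-dose skin score serves as the untreated reference. By contrast, Baseline vital signs (step 6) and the Screening laboratory tests precede dosing.

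Safety is a primary objective of a single-arm study, so the pre-dose state is the natural within-study reference for local tolerability. The Introduction lists application site dermatitis, vesicles and pain among the most common adverse reactions in the adult studies, so this is an expected risk. Redness or swelling that is untreated and does not interrupt dosing is not an AE, so the skin reaction tables are its only route into the report. Pre-existing redness is plausible. Exclusion 17 and the Screening foot examination limit it, but exclusion 6 allows interdigital tinea pedis under an approved topical therapy, and neither check yields a grade.

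**Working it through.** The plan gives no figure for this point, so there is none to reproduce. The check is the order of procedures, then an enumeration of the 0–3 scale.

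**Inputs.** Scale: 0 none, 1 mild, 2 moderate, 3 severe (section 11.2.1). Let *d* be the Day 1 post-dose grade (step 20) and *g* the grade at a later visit. The planned rule counts a subject when *g* > *d*. With a pre-dose grade of 0, the intended rule is *g* > 0.

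**1. Worse-than-baseline count, pre-dose grade 0, reaction present on Day 1 and later.**

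| Day 1 grade | Later 1 | Later 2 | Later 3 |
|---|---|---|---|
| 1 | not counted | counted | counted |
| 2 | not counted | not counted | counted |
| 3 | not counted | not counted | not counted |

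All 9 cells are worse than pre-dose. The planned rule misses 1 + 2 + 3 = 6 of 9.

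Over all 16 pairs (both grades 0–3), the pre-dose rule counts 4 × 3 = 12 and the planned rule counts 3 + 2 + 1 + 0 = 6. The 6 lost pairs are the ones in the table: (1,1), (2,1), (2,2), (3,1), (3,2) and (3,3).

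**2. Visits at which a Day 1 grade 3 subject can never be counted.** Weeks 4 to 48 every four weeks make 12 visits. Adding Week 52 gives 13. Adding Day 29 gives 14 for a PK subject in the 52-week trial. A PK subject in the 4-week trial has 2 (Days 28 and 29).

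**3. Worst score.** It covers the post-baseline period only. Let *g* now be the worst later grade. The reported worst is below the true on-treatment worst whenever *g* < *d*, which is 0 + 1 + 2 + 3 = 6 of 16 pairs.

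These are counts of possible grade pairs, not expected proportions of subjects.

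**4. Illustration in subjects.** The documents give no first-dose reaction rate, so the rate *q* is an assumption. Take *N* = 60 (section 12.8.2), all graded 0 before dosing and all seen at the visit. Assume 25% to 100% of reactors persist at the same or a lower non-zero grade. Expected reactors = 60*q*; shortfall = 60*q* × (0.25 to 1); chance of at least one reactor = 1 − (1 − *q*)^60.

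| Assumed *q* | Reactors | Shortfall at a visit | Chance of ≥ 1 reactor |
|---|---|---|---|
| 2% | 1.2 | 0.3–1.2 | 70% |
| 5% | 3 | 0.75–3 | 95% |
| 10% | 6 | 1.5–6 | 99.8% |
| 20% | 12 | 3–12 | about 100% |

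**The case against.** The step order and the arithmetic are not in dispute. The case on the other side concerns weight and certainty.

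- **A separate SAP may define baseline.** Section 12.8 refers to one, and its text is not in the combined file. It could define the comparison differently or treat Day 1 as on-treatment. That is possible, but it cannot supply a pre-dose grade that no procedure collects.
- **Week 52 is an off-drug score.** It is scheduled four weeks after treatment ends. But it records the worst reaction since the previous visit, it is not a pre-dose state, and 4-week PK subjects and early terminators do not have it.
- **Most of the information is reported elsewhere.** This largely stands. Day 1 grades appear in the by-visit tables, and persisting reactions enter the raw worst and last scores. Week 4 captures the worst reaction since Day 1, and step 19 asks for AEs after the first application. The reactions are omitted from two summaries, not hidden.
- **The size is unknown.** This stands. The pair counts are not frequencies, and the rates in the illustration are assumed.
- **The Day 1 score is not purely on-treatment.** Read literally, the recall rule at Baseline reaches back to Screening, so the score may mix earlier redness with a first-dose effect. That makes it a worse reference.
- **Nothing is decided on this count.** There is no hypothesis test and no decision rule that uses it. That limits the importance of the point but does not make the summary correct.

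**Conclusion.** The concern holds and should be fixed. As written, the worse-than-baseline summary uses an on-treatment reference and misclassifies first-dose redness or swelling that persists at the same or a lower grade. The worst post-baseline score also misses or understates reactions that were worst on Day 1. The comparison problem affects 2 of the 5 signs, since burning, itching and vesiculation are yes/no items.

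The impact is moderate. The summaries are descriptive and the underlying grades stay visible by visit, but they describe a primary safety objective without a control arm. Section 12.7 also repeats every table at the interim analysis, so the error would appear twice.

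The conclusion assumes that baseline means the step 20 score, the only candidate in the procedures. The pair counts in item 1 also assume a pre-dose grade of 0. The number of subjects affected cannot be derived from the documents.

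**What to change.** **New subjects.** Add a local skin reaction score immediately before step 19 of section 11.1.2. Define it as baseline in section 12.1.2 and in the matching synopsis sentence. Align section 11.2.1 and the schedule in Table 1.

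**All subjects.** Treat the step 20 score as the first on-treatment assessment. Label it as post-application in the by-visit tables and include it in the worst on-treatment score.

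**Subjects already enrolled without a pre-dose score.** Drop the worse-than-baseline summary. Report instead any redness or swelling score of 1 or more, or a yes for the other signs, at any time after first dose, counting Day 1 post-application.

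**Cost.** One brief assessment and one eCRF field per new subject; wording only for those already enrolled. There are two downsides: the replacement count may include some redness present before dosing, and the corrected comparison will cover only subjects enrolled after the change, so its denominator must be shown.

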12.1.3 Clinical Laboratory Tests

Results of safety laboratory parameters will be summarized at each study visit using descriptive statistics or frequencies and percentages, as appropriate, for the safety, PK, and non-PK populations. Changes from baseline in safety laboratory values will be summarized by treatment group at Week 48 using descriptive statistics. In addition, changes from baseline in safety laboratory values will be summarized using shift tables according to normal ranges.

12.1.4 Vital Signs

Results of vital sign measurements will be summarized at Weeks 12, 24, 36, and 48 using descriptive statistics or frequencies and percentages, as appropriate, for the safety, PK, and non-PK populations. Changes from baseline in vital sign measurements will be summarized at these visits.

12.1.5 Concomitant Medications

All previous therapies and concomitant medications will be classified based on terminology from the World Health Organization Drug Dictionary. Previous therapies and concomitant medications data will be presented in data listings.

12.1.6 Efficacy for Assessing Treatment Compliance

This primary objective of this study is to assess the safety of the study drug. Descriptive efficacy statistics for the endpoints will assist in evaluating compliance with treatment for the purposes of safety assessment. The efficacy variables evaluated in this study include microscopic KOH examination and mycological culture outcomes of the target great toenail, percent involvement of the target great toenail, growth of the target great toenail, and assessments of the nontarget toenails. The efficacy endpoints include the following:

- Complete Cure, defined as 0% clinical involvement of the target toenail and negative KOH and fungal culture at Week 52
- Complete or Almost Complete Cure at Week 52, defined as :: 5% toenail involvement
- The Clinical Efficacy rate at Week 52, defined as an affected target great toenail area of < 10%
- The Mycologic Cure rate at Week 52, defined as a negative KOH examination and a negative fungal culture of the target great toenail sample

The Complete Cure rate, the Complete or Almost Complete Cure rate, the Clinical Efficacy rate, and the Mycologic Cure rate will be presented using descriptive statistics (sample size n, frequency counts, and percentages) for the safety, PK, and non-PK populations. In addition, the growth of the target great toenail at each study visit and the change from baseline in the number of affected nontarget toenails will be summarized descriptively.

A last observation carried forward (LOCF) imputation will be used to impute missing values for the efficacy variables at Week 52 for the non-PK population analyses. No sensitivity analyses will be conducted.

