12.1.6 Efficacy for Assessing Treatment Compliance

This primary objective of this study is to assess the safety of the study drug. Descriptive efficacy statistics for the endpoints will assist in evaluating compliance with treatment for the purposes of safety assessment. The efficacy variables evaluated in this study include microscopic KOH examination and mycological culture outcomes of the target great toenail, percent involvement of the target great toenail, growth of the target great toenail, and assessments of the nontarget toenails. The efficacy endpoints include the following:

- Complete Cure, defined as 0% clinical involvement of the target toenail and negative KOH and fungal culture at Week 52
- Complete or Almost Complete Cure at Week 52, defined as ≤ 5% toenail involvement
- The Clinical Efficacy rate at Week 52, defined as an affected target great toenail area of < 10%
- The Mycologic Cure rate at Week 52, defined as a negative KOH examination and a negative fungal culture of the target great toenail sample

The Complete Cure rate, the Complete or Almost Complete Cure rate, the Clinical Efficacy rate, and the Mycologic Cure rate will be presented using descriptive statistics (sample size n, frequency counts, and percentages) for the safety, PK, and non-PK populations. In addition, the growth of the target great toenail at each study visit and the change from baseline in the number of affected nontarget toenails will be summarized descriptively.

A last observation carried forward (LOCF) imputation will be used to impute missing values for the efficacy variables at Week 52. No sensitivity analyses will be conducted.

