12.8 Additional Statistical Considerations

All statistical processing will be performed using SAS® version 9.3 or higher unless otherwise stated. No hypothesis testing will be conducted in this study. A statistical analysis plan, describing all statistical analyses, will be provided as a separate document prior to data analysis.

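### Complete or Almost Complete Cure at Week 52 is defined by nail area alone, so a nail with positive KOH or culture can be reported under a cure label

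*Combined protocol and SAP*

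**What the plan says.** Section 12.1.6 of the current protocol lists four Week 52 endpoints for the target great toenail:

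- One joins area and mycology: "Complete Cure, defined as 0% clinical involvement of the target toenail and negative KOH and fungal culture at Week 52".
- The endpoint at issue begins "Complete or Almost Complete Cure at Week 52, defined as" and is completed by an upper limit of 5% on the affected area, with nothing on KOH or culture. The sign before the 5% is misread in the current text as a doubled colon; the first protocol version in the file prints it legibly as ≤.
- One rests on area only and has a clinical name: "The Clinical Efficacy rate at Week 52, defined as an affected target great toenail area of < 10" per cent.
- One rests on the laboratory results only: "The Mycologic Cure rate at Week 52, defined as a negative KOH examination and a negative fungal culture of the target great toenail sample".

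The current synopsis has the same area-only definition of the second endpoint, as do the earlier protocol versions. The last amendment changed the imputation sentence of 12.1.6 and left this definition alone.

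Each rate is to be shown as n, counts and percentages for the safety, PK and non-PK populations. The section plans no table of area against mycology and rules out sensitivity analyses. It also states the purpose: "Descriptive efficacy statistics for the endpoints will assist in evaluating compliance with treatment for the purposes of safety assessment". Section 12.8 adds: "No hypothesis testing will be conducted in this study".

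**The concern.** Within one list, the word cure has two meanings. For Complete Cure and Mycologic Cure it includes negative KOH and negative culture. For Complete or Almost Complete Cure it means a small affected area and nothing more. The list already has a clinical-only endpoint with a clinical name, Clinical Efficacy; the endpoint at issue is a stricter cut of that same measure under a cure label.

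Mycology matters in this study because inclusion criteria 6 and 7 admit only subjects whose target nail is positive on both KOH and dermatophyte culture. A reader who sees a rate headed Complete or Almost Complete Cure will assume that the infection has been shown to be gone, or nearly so. For some of the subjects counted, the study's own laboratory result may say otherwise.

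**Working it through.** The plan states no figure for this endpoint, so there is none to reproduce. The check is one of logic, followed by simple counting.

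**Step 1. Apply the four definitions to every type of nail.** Negative means both KOH and culture negative; positive means either one positive.

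| Involvement | Mycology | Complete Cure | Complete or Almost Complete Cure | Clinical Efficacy | Mycologic Cure |
|---|---|---|---|---|---|
| 0% | negative | yes | yes | yes | yes |
| 0% | positive | no | **yes** | yes | no |
| >0 to 5% | negative | no | yes | yes | yes |
| >0 to 5% | positive | no | **yes** | yes | no |
| >5 to <10% | negative | no | no | yes | yes |
| >5 to <10% | positive | no | no | yes | no |
| ≥10% | negative | no | no | no | yes |
| ≥10% | positive | no | no | no | no |

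The two bold entries are the problem: each counts as a complete or almost complete cure and fails both of the other cure endpoints.

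**Step 2. Express the rates.** Of n subjects, let a have ≤5% and negative mycology, b have ≤5% and positive, c have >5% and negative, and d have >5% and positive.

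- Rate as written: (a + b)/n
- Rate with negative KOH and culture added: a/n
- Difference: (a + b)/n − a/n = b/n
- Mycologic Cure: (a + c)/n

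The rate as written is above Mycologic Cure only if b > c. With the condition added it cannot be, because a ≤ a + c.

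**Step 3. Illustrate the range.** The documents give no values for a, b, c or d. The counts below are assumptions, with n = 40, the approximate non-PK group (60 − 20).

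| a, b, c, d | As written | Mycology added | Difference b/n | Mycologic Cure |
|---|---|---|---|---|
| 8, 0, 12, 20 | 8/40 = 20% | 8/40 = 20% | 0 points | 20/40 = 50% |
| 8, 4, 12, 16 | 12/40 = 30% | 8/40 = 20% | 10 points | 20/40 = 50% |
| 8, 6, 4, 22 | 14/40 = 35% | 8/40 = 20% | 15 points | 12/40 = 30% |
| 5, 10, 2, 23 | 15/40 = 37.5% | 5/40 = 12.5% | 25 points | 7/40 = 17.5% |

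**Step 4. Ask whether the planned tables reveal b.** They do not in general. Suppose, again as an assumption, that a report on 40 subjects shows 14 at ≤5%, 12 Mycologic Cures and 4 Complete Cures. Then a is at least 4 (every Complete Cure is in a) and at most 12 (every member of a is a Mycologic Cure). So b = 14 − a lies anywhere from 14 − 12 = 2 to 14 − 4 = 10.

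**The case against.** The best defence is that little depends on this endpoint. The primary objectives are safety and PK, the efficacy rates are descriptive aids to the compliance and safety assessment, nothing is tested, and the sample size was not calculated from any of them. The definition is also explicit, and Complete Cure and Mycologic Cure are tabulated alongside it. All of that stands and limits the weight of the point. It does not remove it: with no test to report, the label carries the message, and Step 4 shows that the accompanying rates do not recover the missing joint count.

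A second defence is that the full definition may sit elsewhere. Section 12.8 refers to a separate statistical analysis plan, whose text is not in the file, so a mycology condition there cannot be excluded. That lowers confidence, but the protocol would still need to agree with it.

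Third, tightening a definition during an open-label study is more than an edit of wording. That is fair, and is why the area-only rate should be kept.

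Several stronger readings are tempting and are not supported:

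- *The endpoint counts nails that are still growing fungus.* That fits only culture-positive nails. KOH is a microscopic examination for hyphae, so a KOH-positive, culture-negative nail has not been shown to grow anything.
- *The rate will exceed the mycologic cure rate.* It can, if b > c, but the documents give no basis for expecting it. Clinical Efficacy could exceed it too.
- *The endpoint fails to contain Complete Cure.* It does contain it; the fault lies in the mycology-positive nails that it also admits.

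**Conclusion.** The point holds on the text. By the definition in 12.1.6 and the synopsis, a nail with 0 to 5% involvement and positive KOH or culture counts as a complete or almost complete cure, although the plan's other two cure endpoints both reject it. The excess over the mycologically confirmed rate is exactly b/n. It ranges from zero, if every nail at ≤5% is negative, up to the whole reported rate, if none is. No size within that range can be defended from the documents, and the 0 to 25 points in the illustration come from assumed counts, not from an estimate of bias.

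The consequence is a mislabelled descriptive rate. No error rate, sample size or primary objective is affected. It is worth correcting before analysis, but it is not a serious flaw in the study. The conclusion assumes that the unseen analysis plan does not already add the mycology condition.

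**What to change.** In 12.1.6 and in the synopsis, define Complete or Almost Complete Cure at Week 52 as involvement of the target great toenail of 5% or less together with a negative KOH examination and a negative fungal culture. Keep the prespecified area-only rate, renamed *complete or almost complete clinical clearance*, so that nothing already planned is lost. Add one table of involvement (≤5%, >5%) by mycology (negative, positive) at Week 52 for each population.

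No data collection changes. Table 1 schedules the target nail assessment, KOH and culture together at Weeks 12, 24, 36, 48 and 52, so the joint outcome is available at the same post-baseline visits as the area.

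The costs are a cure figure that is lower or at best equal, one extra table, and a dated justification for the change because the study is open label. If the separate analysis plan already contains the condition, the change reduces to aligning the protocol with it.
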